3.2 Overview of LiteCure Laser System

The EXPi device is a research device based on LiteCure's EXPi Deep Tissue Laser Therapy™ system. For this research study, the EXPi system's beam delivery, Empower™, is modified to deliver NIR laser energy non-invasively to the brains of subjects diagnosed with neuropsychiatric disorders. Other than the cap, the EXPi device is the same device as LiteCure's EXPi system: model LTS-2500, which is marketed under FDA 510(K) # K173067. The device is manufactured and supplied by LiteCure LLC, [name].

The EXPi device is a Class II medical device according to 21 CFR 890.5500 and 878.4810 and is manufactured according to 21 CFR 820. It uses laser diode sources that emit in the near infrared (808 +/- 10 nm) with a maximum continuous output of ≤ 30 watts. The device consists of two main assemblies: a console and an optical delivery system. Laser power is generated and controlled within the console assembly and delivered to the optical delivery system: custom helmet (cap), via a flexible double-clad optical fiber. The cap is configured to produce a 4 cm diameter (12 cm²) beam of light at each of two sites on the subject's forehead: adjustable at/near EEG locations F3 and F4.

The console is programmed to produce laser energy in one of 4 modes:

1. Mode 1 (BCW group), NIR-TLT dose:
 - i. Treatment site(s): EEG F3 and F4
 - ii. Time format:
continuous wave
 - iii. Average radiance: 350 mW / cm²
 - iv. Exposure time: 429 sec.
 - v. Total fluidity delivered: 3.6 kJ (1.8 kJ per treatment location)
2. Mode 2 (BPW-1 group), NIR-TLT dose:
 - i. Treatment site(s): EEG F3 and F4
 - ii. Time format: wave
pulsed, 10 Hz; 50% duty cycle
 - iii. Average radiance: 350 mW / cm²
 - iv. Exposure time: 429 sec.
 - v. Total fluidity delivered: 3.6 kJ (1.8 kJ per treatment location)
3. Mode 3 (BPW-2 group), NIR-TLT dose:
 - i. Treatment site(s): EEG F3 and F4
 - ii. Time format: pulsed wave, 40-50 Hz; 50% duty cycle
 - iii. Average radiance: 350 mW / cm²

Near Infrared Transcranial Laser Therapy in Subjects with Major Depressive Disorder: A study of Dosing with Laser.

- iv. Exposure time: 429 sec.
- v. Total fluidity delivered: 3.6 kJ (1.8 kJ per treatment location)

4. Mode 4 (SHAM group), NIR-TLT dose:

- i. Treatment site(s): none
- ii. Time format: none
- iii. Average radiance: 0 mW / cm²
- iv. Exposure time: 429 sec.
- v. Total fluidity delivered: 0 kJ

See section 4.3 - Dosing rationale

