The console display does not provide information on the dose irradiance, showing only the mode number, e.g. Mode 1 and, although the laser exposure varies with the treatment mode, to maintain blinding, the treatment time will be the same in all modes: 429 seconds (7.15 minutes). In addition, the behavior of the device, the performance/output of all visible and audible indicators, including the graphical user interface, is identical in all modes, differing only with respect to treatment irradiance. Since the laser radiation emitted during the NIR mode is invisible to the naked eye, the modes cannot be distinguished from each other, which keeps the operator and subject blinded to the group tasks.

Dose administration for the present trial will follow the specifications: wavelength 830 nm; mean irradiance 54.8 mW / cm²; mean fluence 65.8 J / cm² (according to the parameters used in the ELATED-2 study in MGH with the Omnilux New U device), which demonstrated in terms of improvement of depressive symptomatology evaluated with HAMD17 in patients with major depression. Therefore, by virtue of the ELATED2 findings, doses were considered for this intervention in patients with MDD.

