4.1 Study Aims

Primary Aim:

A. To evaluate and compare the effect(s) of each of the four doses of NIR-TLT on depressive symptomatology: antidepressant effect, in patients with major depressive disorder (MDD).

Hypothesis 1: Total HAM-D 17 scale scores will vary in a NIR-TLT dose-dependent manner, with BPW dose being more effective.

We also expect to be able to estimate the effect size of the antidepressant action as a function of the irradiance applied to the NIR-TLT skin, with the BPW dose being more effective.

Secondary Aims:

B. Compare safety and tolerability at each dose of NIR-TLT.

Hypothesis 2: The doses of NIR-TLT tested in this study will be safe and well tolerated by patients with MDD, as assessed by SAFTEE-SI and reports of serious adverse events. We do not anticipate dose-dependent differences in reported side effects.

C. To compare the effect(s) of each of the four doses of NIR-TLT on brain electrophysiology.

Exploratory Aim:

D. To describe the findings visualized in PET, related to the brain metabolism of the participants, before and at the end of the intervention under study.

4.2 Rationale for the use of the EXPi device:

Transcranial photobiomodulation (t-PBM) with near infrared (NIR) laser therapy has emerged as a possible antidepressant treatment in both animal models (Mohammed et al.2016; Salehpour 2016-2017; Xu et al.2017; Wu et al.2012), and in human studies (Cassano 2015- 2017; Caldieraro et al.2018) t-PBM. NIR appears to increase brain metabolism (by activating the cytochrome C oxidase in the mitochondria), to increase neuroplasticity and to modulate the

Near Infrared Transcranial Laser Therapy in Subjects with Major Depressive Disorder: A study of Dosing with Laser.

endogenous opioids, while decreasing inflammation and oxidative stress. (Chung et. al. 2012; Yu et. al. 1997; Oron et al. 2007, Mochizuki et al. 2002) t-PBM penetrates deep into the cerebral cortex, modulates cortical excitability, and improves cerebral perfusion and oxygenation. The safety of t-PBM has been studied in a sample of 1410 acute stroke patients, with no significant difference in adverse event rates between t-PBM and sham exposure. (Hacke et al. 2014; Lamp et al. 2007, Zivin et al. 2009) Uncontrolled studies suggest an antidepressant effect of t-PBM in subjects suffering from MDD (Cassano 2015-2017; Caldieraro et al. 2018).

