4.4 Study Design

This study is a multicenter, randomized, sham-controlled, double-blind study on the use of transcranial continuous light therapy as a treatment for depressive symptoms in patients with major depressive disorder (MDD). Laser light therapy is tested in a strict parallel design.

This study will include 112 subjects randomly assigned to each of the four NIR-TLT treatment groups (28 subjects/group).

All subjects will receive three NIR-TLT treatments per week for 6 weeks and will complete a follow-up evaluation two weeks after treatment completion. All subjects and investigators (except the study statistician) will be blinded to treatment sequence assignment.

Energy will be administered at a wavelength of 808 nm, bilaterally to two frontal areas on the left and right side of the forehead, at or near electroencephalography sites F3 and F4. To maintain blinding, the treatment duration will be 429 seconds (7.15 minutes) for all groups. The treatment exposure (time during which the laser is active for the duration of the treatment) will be specific for each group, controlled by the device to normalize the treatment fluence of each active session per treatment location. Treatment will follow these specifications: wavelength 830 nm; average irradiance 350 mW / cm²; average fluence of 65.8 J / cm² (according to the parameters used in the ELATED-2 study at MGH with the Omnilux New U device) being the total fluence delivered: 3.6 kJ (bilateral) or 1.8 kJ (unilateral), either on the subject's forehead, at or near electroencephalography (EEG) sites F3 and F4.

The entire session (which includes the 429-second treatment and all procedures described in the "Study Visits" section) is estimated to take 30 minutes or less (Schiffer et al., 2009) (Lampl et al., 2007, Zivin et al., 2009). Additional time is needed to prepare the subject, fit the necessary protections (e.g., goggles), inspect the subject's skin, set up the NIR-TLT devices, and give the subject time to rest after irradiation. NIR-TLT treatment will only be administered by trained personnel who are on study staff. All personnel administering the treatment must pass laser safety training created by the American Institute for Medical Laser Applications and approved by the relevant Committees. The duration of irradiation will be decreased if clinically indicated, based on tolerability as needed.

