5.2 Aims of the Study

Primary Aims:

A. To compare the effect(s) of each of the four doses of NIR-TLT on depression symptomatology: antidepressant effect.

Hypothesis 1: Total HAM-D 17 scores will vary in a NIR-TLT dose-dependent manner, with BPW dose being more effective.

We also expect to be able to estimate the effect size of the antidepressant action as a function of the irradiance applied to the NIR-TLT skin, with the BPW dose being more effective.

B. Compare the safety and tolerability of each dose.

Hypothesis 2: The doses of NIR-TLT tested in this study will be safe and well tolerated by patients with MDD, as assessed by SAFTEE-SI and serious adverse events.

We do not anticipate dose-dependent differences in reported side effects.

Secondary Aims:

C. To compare the effect(s) of each of the four doses of NIR-TLT on brain electrophysiology.

D. To compare the effect(s) of each of the four doses of NIR-TLT on mitochondrial function.

Transcranial Near Infrared Laser Therapy in Subjects with Major Depressive Disorder: A Laser Dosing Study.

E. To study the correlations (correlating) antidepressant effects, brain electrophysiology and mitochondrial function of each of the NIR-TLT doses.

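### The active modes share one average irradiance, so effect size cannot be estimated as a function of irradiance beyond active versus sham; the laser specification in 1, 3.2 and 4.4 is also inconsistent

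*Protocol*

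**What the plan says.** **Aim.** Protocol 4.1 and 5.2 both carry Hypothesis 1, in 5.2 as "Total HAM-D 17 scores will vary in a NIR-TLT dose-dependent manner, with BPW dose being more effective". Both then add an expectation. Section 4.1 words it as "We also expect to be able to estimate the effect size of the antidepressant action as a function of the irradiance applied" to the skin, and 5.2 likewise expects to "estimate the effect size of the antidepressant action as a function of the irradiance applied to the NIR-TLT skin". Both again name the pulsed (BPW) dose as the more effective one.

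**Modes.** The mode list in 3.2 gives Modes 1, 2 and 3 the same line, "Average radiance: 350 mW / cm²", the same 429 s exposure and the same 3.6 kJ (1.8 kJ per site). The three differ in waveform: continuous, 10 Hz, and 40-50 Hz, the pulsed modes at 50% duty cycle. Sham is 0 mW/cm² and 0 kJ. Section 4.4 adds that laser-active time is group-specific, "controlled by the device to normalize the treatment fluence of each active session per treatment location". On blinding, 3.2 describes the modes as "differing only with respect to treatment irradiance".

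**Laser specification.**
- Section 1: 830 nm, 54.8 mW/cm², 65.8 J/cm² and 3.6 kJ bilateral.
- 3.2, device and mode list: 808 ± 10 nm, 350 mW/cm², 429 s, and two beams of 12 cm² each.
- 3.2, closing paragraph: "wavelength 830 nm; mean irradiance 54.8 mW / cm²; mean fluence 65.8 J / cm²".
- 4.4: 808 nm, and later in the same paragraph 830 nm with 350 mW/cm², 65.8 J/cm² and 3.6 kJ.

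Sections 1, 3.2 and 4.4 credit their parameters to ELATED-2. Section 3.1 describes that study as 823 nm, 36.2 mW/cm² and up to 65.2 J/cm².

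**The concern.** A response can be estimated as a function of a quantity only if the arms vary it. Here the arms were built to hold average irradiance and energy fixed and to vary the waveform. The sentence in 4.1 and 5.2 promises something that the design does not deliver for average irradiance, the only irradiance the mode list states. It also cannot support its own ending: pulsed and continuous modes are equal on average irradiance, so one cannot outperform the other as a function of it.

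The second issue concerns the record of what was given. In a trial titled as a dosing study, the laser parameters are the intervention. A report or review that takes them from Section 1 or the end of 3.2 would cite a dose that the programmed modes do not produce.

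**Working it through.** **Inputs.** From the 3.2 mode list: average irradiance 350 mW/cm² (Modes 1-3) and 0 (Mode 4), 429 s, 12 cm² per site at two sites (24 cm²), 3.6 kJ, and 50% duty cycle for pulsed modes. From 1, the end of 3.2, and 4.4: 65.8 J/cm², 54.8 or 350 mW/cm², and 830 nm.

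**Step 1: reproduce the stated energy.** Fluence = irradiance × time; energy = fluence × area.
- 0.350 W/cm² × 429 s = 150.15 J/cm²
- 150.15 × 12 cm² = 1,802 J, or 1.8 kJ per site
- 1,802 × 2 = 3,604 J, or 3.6 kJ

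The mode list reproduces its own energy. (A 4 cm disc is strictly 12.57 cm². Then 1,800 / 12.57 = 143 J/cm², and the conclusion is the same.)

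**Step 2: test the stated 65.8 J/cm².**

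| Stated irradiance | Fluence in 429 s | Energy over 24 cm² | Time needed for 65.8 J/cm² |
|---|---|---|---|
| 350 mW/cm² | 150 J/cm² | 3.60 kJ | 65.8 / 0.350 = 188 s |
| 54.8 mW/cm² | 23.5 J/cm² | 0.56 kJ | 65.8 / 0.0548 = 1,201 s |

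Neither irradiance gives 65.8 J/cm² in 429 s. Nor does 65.8 J/cm² give the stated energy: 65.8 × 24 = 1,579 J (1.58 kJ), and 3.6 kJ would need 3,600 / 65.8 = 54.7 cm². The ratios are 150.15 / 65.8 = 2.28 for fluence (implied against stated) and 350 / 54.8 = 6.39 for irradiance (between sections).

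The pair 54.8 and 65.8 fits 20 minutes (0.0548 × 1,200 = 65.76). That suggests values carried over from a longer session, but this is an inference; the mismatch itself is not.

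**Step 3: wavelength.** The device's upper limit is 808 + 10 = 818 nm, and 830 − 818 = 12 nm outside it.

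**Step 4: what average irradiance can identify.** The four arms sit at 350, 350, 350 and 0. With two distinct values, a polynomial design in irradiance has rank 2 whether its degree is 1, 2 or 3. Among the active arms alone the rank is 1. The only slope available is (active mean − sham mean) / 350, which is the active-versus-sham contrast rescaled.

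**Step 5: what peak irradiance can identify.** The protocol does not state peak values.
- If 350 is the time average, the pulsed peak is 350 / 0.5 = 700 mW/cm². Over 24 cm² that is 0.7 × 24 = 16.8 W, within the 30 W limit.
- If 350 were the on-phase value, the average would be 175 mW/cm², the fluence 0.175 × 429 = 75.1 J/cm² and the energy 75.1 × 24 = 1.80 kJ, half the stated figure.

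The stated energy therefore requires the first reading, with peaks of 0 (sham), 350 (continuous), 700 and 700 (both pulsed). Among active arms, 700 against 350 is the same contrast as pulsed against continuous.

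**The case against.** The strongest reply is that 4.1 and 5.2 say irradiance, not average irradiance. Equal fluence with group-specific laser-active time means that on-phase irradiance differs, and three peak levels can be fitted. That stands as far as it goes: a reader who infers that no irradiance-based estimate of any kind exists would be going too far. But the peak is never stated, is identical in the two pulsed arms, and cannot be separated from pulsing. The result would be a comparison of waveforms under another name.

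It is also fair that the 3.2 sentence on how modes differ belongs to a blinding argument. Since instantaneous irradiance does differ between pulsed and continuous modes, that sentence is imprecise rather than plainly false.

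A reader might infer from the 2.3-fold gap that fluence differs between sections. It does not. Every section that states this trial's fluence gives 65.8 J/cm²; the 150 is implied by the mode list and printed nowhere. Only irradiance and wavelength conflict between statements.

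Finally, the operative settings can largely be recovered. The mode list is coherent. Table 1 lists this trial at a maximum of 350 mW/cm², 7 minutes and 2 sites, and 4.9.2 specifies safety glasses at 808 nm. The protocol mostly uses dose to mean mode. The irradiance expectation is absent from the Section 1 objectives, and no analysis in 5.5 uses it. This limits the harm but leaves the wrong text in place.

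**Conclusion.** The point holds in two parts.

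1. For average irradiance, the expectation in 4.1 and 5.2 cannot be met beyond active versus sham. For peak irradiance, any estimate is fully confounded with pulsing. The peak figures assume that 350 mW/cm² is the time average, as the stated energy requires. Dose-dependent in Hypothesis 1 is defensible only if dose means mode.
2. The operative specification is inconsistent: irradiance differs 6.4-fold between sections, 830 nm lies outside the device range, and the stated fluence is exceeded 2.3-fold by what the mode list implies. The parameters credited to ELATED-2 also differ from those in 3.1. The documents do not show which ELATED-2 set is right, so only the mismatch is claimed.

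A reader might infer that the primary result or participants' treatment is compromised. The documents do not support that. The repeated-measures ANCOVA in 5.5 compares groups and does not use irradiance, and the console is programmed by mode, so the risk of wrong delivery is low. The consequence is an unsupported dose-response claim and a possibly misreported dose.

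**What to change.** **Aims (4.1, 5.2).** Delete the effect-by-irradiance sentence. State that HAM-D-17 change is compared between stimulation modes, including sham, at equal average irradiance and energy across the active modes. Keep the expectation that pulsed modes do better only as a descriptive or exploratory statement. The four-group group-by-time interaction in 5.5 can be significant from active against sham alone, so it does not test pulsed superiority.

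**Blinding text (3.2).** Say that the active modes differ in waveform and that sham emits no laser energy.

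**Specification (1, 3.2, 4.4).** Give one set of values, confirmed by the sponsor against the device settings. The documents imply 808 nm, 350 mW/cm² average, 429 s, about 150 J/cm², 1.8 kJ per site and 3.6 kJ in total. State the peak irradiance for the pulsed modes (700 mW/cm² if 350 is the time average). Remove the attribution of these values to ELATED-2.

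**Cost.** Wording in an amendment, plus the sponsor's check of the settings. Arms, sample size, device programming and the 5.5 analysis do not change. The downside is that the claim narrows from dose-response to a comparison of modes.

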4.3 Dosing Rationale

The laser dose to be used in the present clinical trial is derived from previous clinical experience with the use of other versions of the medical device in studies conducted in patients with acute stroke, major depressive disorder and Alzheimer's disease in whom lasers have been administered with this device, which has provided guidance on safe and potentially effective doses in the study population. A summary of this information is presented in Table 1.

Laser devices have a potential risk of retinal injury when used incorrectly; this is mitigated by the use of protective eye equipment "goggles" and proper procedures to ensure eye safety (Barkana & Belkin, 2000).

No serious adverse events were found in our literature review (Caldieraro & Cassano, 2019). Two open-label studies using 1 and 6 sessions of t-PBM reported no treatment emergent side effects (Cassano et al., 2015; Schiffer et al., 2009).

The safety of a t-PBM session was evaluated in three large RCTs with a combined sample of 1410 stroke subjects (Hacke et al., 2014; Huisa et al., 2013; Lampl et al., 2007). No significant differences in the rate of adverse effects were observed between the group receiving NIR laser (808 nm; 5W, 700 mW / cm²) or sham.

A clinical trial with 16 sessions of t-PBM reported a higher number of mild side effects in the active treatment group, the most frequent being insomnia, "seeing bright colors," "an ashtray taste," and irritable mood (Cassano et al., 2018, p. 2). Other potential risks are related to improper administration and will be mitigated by safety procedures, such as the use of protective eyewear.

The risk of thermal injury from PBM administered with the parameters used in the studies we reviewed is considered minimal and limited to the skin. In ten people treated by TBI with 10-15 W lasers, a much higher power than that used in t-PBM, skin temperature increased to no more than 30°C with rapid cooling after removal of the NIR light. Clinically, patients reported slight skin heating, but no discomfort (Morries et al., 2015).

Near Infrared Transcranial Laser Therapy in Subjects with Major Depressive Disorder: A study of Dosing with Laser.

TITLE	PUBLISHED					NOT PUBLISHED			PRESENT
	NEST	NEST-2	NEST-3	ELATED	ELATED-2	ELATED-3	TRIADE	TRAP-AD	"ELATED-4"
Infrared laser therapy for ischemic stroke: a new treatment strategy: results of the NeuroThera Effectiveness and Safety Trial-1 (NEST-1)	Effectiveness and Safety Trial of a New Ischemic Stroke Treatment Within 24 Hours From Stroke Onset (NEST-2)	Efficacy and Safety Trial of Transcranial Laser Therapy Within 24 Hours From Stroke Onset (NEST-3)	Transcranial Laser Therapy for Major Depressive Disorder	Transcranial Photobiomodulation for the Treatment of Major Depressive Disorder. The ELATED-2 Pilot Trial	Transcranial Laser Therapy, Continuous and Pulsed Light, for Major Depressive Disorder (ELATED-3)	Transcranial Near Infrared Radiation and Cerebral Blood Flow in Depression	Transcranial Photobiomodulation for Alzheimer's Disease (TRAP-AD)	Near-infrared Transcranial Laser Therapy in Subjects with Major Depressive Disorder: A study of Dosing with Laser	
LOCATION	GLOBAL	GLOBAL	GLOBAL	MGH/Harvard	MGH/Harvard	MGH/Harvard	MGH/Harvard NYU NKI	MGH/Harvard NYU NKI	LIMA
INDICACIÓN	ACUTE STROKE	ACUTE STROKE	ACUTE STROKE	MAJOR DEPRESSIVE EPISODE	MAJOR DEPRESSIVE EPISODE	MAJOR DEPRESSIVE EPISODE	MAJOR DEPRESSIVE EPISODE	ALZHEIMER'S DISEASE	MAJOR DEPRESSIVE EPISODE
Effectiveness	YES	NO	NO	YES	YES	NO	ONGOING	ONGOING	ONGOING
SECURITY	YES (NO SAE)	YES (NO SAE)	YES (NO SAE)	YES (NO SAE)	YES (NO SAE)	YES (NO SAE)	ONGOING	ONGOING	ONGOING
IRRADIANCE (mW/cm ²)	700	700	700	700	~50	~50	Multiple groups Max 770	Multiple groups Max 300	Multiple groups Max 350
EXPOSURE TIME (min)	2	2	2	2	25	25	~6	~11	7
NUMBER OF SITES	20	20	20	4	2	2	2	2	2

Table 1 - Summary of doses and efficacy and safety results in previous studies. Source: Lampl et al. (2007), Huisa et al. (2013), Zivin et al. (2014), Cassano (2017), Cassano et al. (2018), Cassano (2016), NIMH (2021), NYU (2021).

Near Infrared Transcranial Laser Therapy in Subjects with Major Depressive Disorder: A study of Dosing with Laser.

4.4 Study Design

This study is a multicenter, randomized, sham-controlled, double-blind study on the use of transcranial continuous light therapy as a treatment for depressive symptoms in patients with major depressive disorder (MDD). Laser light therapy is tested in a strict parallel design.

This study will include 112 subjects randomly assigned to each of the four NIR-TLT treatment groups (28 subjects/group).

All subjects will receive three NIR-TLT treatments per week for 6 weeks and will complete a follow-up evaluation two weeks after treatment completion. All subjects and investigators (except the study statistician) will be blinded to treatment sequence assignment.

Energy will be administered at a wavelength of 808 nm, bilaterally to two frontal areas on the left and right side of the forehead, at or near electroencephalography sites F3 and F4. To maintain blinding, the treatment duration will be 429 seconds (7.15 minutes) for all groups. The treatment exposure (time during which the laser is active for the duration of the treatment) will be specific for each group, controlled by the device to normalize the treatment fluence of each active session per treatment location. Treatment will follow these specifications: wavelength 830 nm; average irradiance 350 mW / cm²; average fluence of 65.8 J / cm² (according to the parameters used in the ELATED-2 study at MGH with the Omnilux New U device) being the total fluence delivered: 3.6 kJ (bilateral) or 1.8 kJ (unilateral), either on the subject's forehead, at or near electroencephalography (EEG) sites F3 and F4.

The entire session (which includes the 429-second treatment and all procedures described in the "Study Visits" section) is estimated to take 30 minutes or less (Schiffer et al., 2009) (Lampl et al., 2007, Zivin et al., 2009). Additional time is needed to prepare the subject, fit the necessary protections (e.g., goggles), inspect the subject's skin, set up the NIR-TLT devices, and give the subject time to rest after irradiation. NIR-TLT treatment will only be administered by trained personnel who are on study staff. All personnel administering the treatment must pass laser safety training created by the American Institute for Medical Laser Applications and approved by the relevant Committees. The duration of irradiation will be decreased if clinically indicated, based on tolerability as needed.

